8.3.1 Time period and frequency for collecting AE, AESI, and SAE information

For trial subjects enrolled in this clinical trial, i.e., after transfer from the parent trial to this trial, all AEs, AESI, and SAEs (including a death) will be recorded at the time points listed in the SoA in Section 1.3. All safety reporting will occur through this rollover trial; this includes the reporting of non-vaccine related AEs that are unresolved from the parent trial.

For subjects who receive a non-trial SARS-CoV-2 vaccination, AEs/SAEs will be collected as specified above until the date when the subject was vaccinated with the non-trial SARS-CoV-2 vaccine. The AEs expected to be captured after non-trial SARS-CoV-2 vaccination are within the frame of post-marketing safety data reporting.

Investigators are not obligated to actively seek AEs or SAEs at any time after a trial subject has been discharged from the trial, however, if the investigator learns of any SAE (including a death), that they consider to be reasonably related to the IMP administration or trial participation, the investigator must promptly notify the sponsor.

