8.3.3 Follow-up of AEs and SAEs

After the initial AE/SAE report, the investigator is required to proactively follow each trial subject at subsequent visits/contacts. All AEs/SAEs will be followed until resolution, stabilization, the event is otherwise explained, or the trial subject is lost to follow-up (as defined in Section 7.3). Further information on follow-up procedures is provided in Section 10.3.1.7.

BioNTech SE
Confidential

Clinical Trial Protocol BNT162-14 Page 51 of 91 Version: 4.0 Date: 20 JAN 2022

The investigator is obligated to perform or arrange for the conduct of supplemental measurements and/or evaluations as medically indicated or as requested by the sponsor to elucidate the nature and/or causality of the AE or SAE as fully as possible. This may include additional laboratory tests or investigations, histopathological examinations, or consultation with other healthcare professionals.

New or updated information will be recorded in the originally completed CRF.

The investigator must submit any updated SAE data to the sponsor within 24 h of receipt of the information as indicated in Section 10.3.1.10.

All ongoing AEs/SAEs will be followed until resolution, considered by the investigator to be stable or chronic (resolved with sequelae), the trial subject is lost to follow-up or the trial subject withdraws consent. If no final status is reached by the time the trial subject is discharged from the trial, the investigator must confirm the unavailability of a final status.

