10.3.1 Definition of AE and TEAE

- An AE is any untoward medical occurrence in a trial subject, temporally associated with the use of trial treatment, whether or not considered related to the IMP.
 NOTE: An AE can therefore be any unfavorable and unintended sign (including an abnormal laboratory finding that is clinically significant), symptom, or disease (new or exacerbated) temporally associated with the use of IMP.
- Events after signing ICF and before IMP administration will be handled as AEs (also called pre-existing conditions).
- A TEAE is defined as any AE with an onset after the first IMP injection or worsened after the first IMP injection (if the AE was present before the first administration of IMP). AEs with an onset date more than 28 d after the last administration of IMP will be considered as treatment-emergent only if assessed as related to IMP by the investigator.

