6.4.3. Adverse events

Definition

For detailed information on adverse events see Section 10.3 of the protocol. Solicited AEs that are recorded from the subject diaries on the reactogenicity CRFs will not be reported as AEs unless the solicited AE meets criteria for SAE or begins after Day 8 or started before Day 8 and continues past Day 8.

Adverse events (AEs) will be coded using the Version MedDRA[®] 24.0 to get a system organ class (SOC) and preferred term (PT) for each AE.

A TEAE is defined as any AE with an onset after the first injection (Dose 1) (if the AE was absent before the first injection) or worsened after the first injection (Dose 1) (if the AE was present before the first injection (Dose 1)). AEs with an onset date more than 28 days after the last injection will be considered as treatment emergent only if

assessed as related to IMP by the investigator. AEs that cannot be determined to not be treatment emergent due to missing date or time will be defined as TEAE.

Note: To clarify the definition in the protocol, AEs with an onset date at the date of the first injection (Dose 1) will only be considered as treatment emergent if the AE occurred after the first injection (Dose 1). AEs with missing time and occurring on the day of Dose 1 or AEs with missing date will be analyzed as treatment emergent.

TEAEs will be evaluated for following time interval and groups:

- Up to 28 days after the first IMP injection (Group A and immunology subset of Group B)
- After the first IMP injection up to 28 days after the second IMP injection (immunology subset of Group B non-transplant)
- After the second IMP up to 28 days after the second IMP injection (immunology subset of Group B transplant)
- All TEAEs (Group A and immunology subset of Group B)

AEs are assigned to the time interval according to their start date and time. AEs with missing date will be assigned to each of the respective intervals if it cannot be ruled out, that it belongs to the time interval.

Adverse events of special interest (AESIs)

The following events will be reported as AESIs: myocarditis, pericarditis, anaphylaxis, thromboembolic events (e.g., deep vein thrombosis, stroke, myocardial infarction), immune thrombocytopenia and immune based neurologic events (e.g., optic neuropathy, Guillain-Barré syndrome). AESIs are recorded in the CRF.

AESIs and SAEs will be evaluated up to 26 weeks after the ICF was signed for all groups.

Analysis

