The following TEAE types will be analyzed for Group A and the immunology subset of Group B:

- Any TEAE
- Related TEAE, i.e., suspected unexpected serious adverse reactions (SUSARs) which will be described in safety reports
- Any Grade ≥3 TEAE
- Any related Grade ≥3 TEAE
- Any treatment emergent serious adverse event (TESAE)
- Related TESAE
- TEAESI

- TEAEs linked to confirmed COVID-19 cases (TEAEs with preferred term = 'COVID-19')
- Deaths

The following AE types will be analyzed for all groups if applicable:

- Any AE
- Related AE
- Any Grade ≥3 AE
- Any related Grade ≥3 AE
- Any serious adverse event (SAE)
- Related SAE
- AESI
- Related AESI
- Any AEs linked to confirmed COVID-19 cases (AEs with preferred term = 'COVID-19')
- Deaths

Overall summary of TEAEs

For Group A and the immunology subset of Group B, the number and percentage of subjects reporting at least one TEAE and the number of TEAEs will be summarized for all TEAE types defined above overall.

For Group B, the number and percentage of subjects reporting at least one

- SAE
- AESIs

will be summarized.

For Group A and the immunology subset of Group B, the number and percentage of subjects reporting at least one TEAE and the number of TEAEs will be summarized by PT nested within SOC for each of the following AE types: Any TEAE, Related TEAE, Any TESAE, Related TESAE, TEAEs leading to treatment discontinuation, solicited TEAEs and fatal TEAE.

For Group B, the number and percentage of subjects reporting at least one TESAE will be summarized by PT nested within SOC.

If a SOC and PT is reported more than once for a subject, the subject will only be counted once for this SOC and PT at the worst grade level. All TEAE summary tables will be sorted alphabetically by SOC and PT within SOC.

TEAE by grade

For Group A and the immunology subset of Group B, the number and percentage of subjects with TEAEs and TESAEs will be summarized by worst grade by PT nested within SOC by time interval.

For Group B, the number and percentage of subjects with TESAEs will be summarized by worst grade by PT nested within SOC.

The worst grade will be counted if a TEAE is reported more than once by the same subject for this SOC and PT.

AEs

The number and percentage of subjects reporting at least one AE and the number of AEs will be summarized for the above defined AE types for all groups.

SAEs

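### SAP 6.4.3 counts worsened AEs as treatment emergent but places them in the 28-day intervals by start date, so single-record worsenings can be missed or misplaced

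*SAP*

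**What the plan says.** SAP 6.4 makes the proportion of subjects with at least one unsolicited TEAE in the 28 days after each injection a primary endpoint.

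SAP 6.4.3 and Protocol 10.3.1 define a TEAE in two ways. Either the event starts after the first injection, or it was already there and "worsened after the first injection (Dose 1"). The protocol's wording of the second route is "worsened after the first IMP injection (if the AE was present before the first administration of IMP").

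SAP 6.4.3 then lists four intervals:

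1. "Up to 28 days after the first IMP injection (Group A and immunology subset of Group B"). No start point is written.
2. Non-transplant immunology subset: from after the first injection to 28 days after the second.
3. Transplant subjects: from after the second injection to 28 days after it.
4. All TEAEs, without a date limit, for Group A and the immunology subset.

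The placement rule is "AEs are assigned to the time interval according to their start date and time". An event with a missing date goes into every interval to which it might belong. Nothing is said about the date of worsening. For Group A and the immunology subset, TEAEs are also "summarized by worst grade by PT nested within SOC by time interval".

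AE records with a start before Dose 1 can exist. Protocol 10.3.1 handles events between consent and injection as AEs. Protocol 8.3.1 moves all safety reporting into this trial and says that "this includes the reporting of non-vaccine related AEs that are unresolved from the parent trial". On follow-up, Protocol 8.3.3 says "New or updated information will be recorded in the originally completed CRF".

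**The concern.** The second route to TEAE status is needed only for a record that starts before Dose 1, because anything starting later already qualifies by onset. The date that makes such an event treatment emergent is the date of worsening, yet the event is placed by its start date. A similar mismatch arises at Dose 2 for an event that began between the injections and became worse after the second.

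At stake is a primary safety proportion and the dose to which severity is attributed. Exacerbation of an ongoing condition after a further dose is of particular interest in the transplant and HIV-positive subjects. The safety of the fourth vaccination in transplant subjects is a stated purpose of the current protocol (section 2.2). The SAP is also uneven here: an event of unknown date is placed in every possible interval, while an event known to have worsened after a dose may be in none of the dated ones.

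**Working it through.** The plan states no figure that depends on this rule, so there is nothing to reproduce. The check applies the written rule to test events.

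Let Dose 1 be time 0, Dose 2 be time d, and s the recorded start, all in days.

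- Interval 1, literal: s ≤ 28. Interval 1, post-injection: 0 < s ≤ 28.
- Interval 2 (non-transplant): 0 < s ≤ d + 28.
- Interval 3 (transplant): d < s ≤ d + 28.
- Interval 4: any TEAE.

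Assumed for illustration: d = 21 for non-transplant subjects; d = 150 for transplant subjects, which is 150/30.25 = 5.0 months on the SAP's conversion and so inside the 3-to-7-month window. Intervals 2 and 3 are shown where they apply to the group.

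| Event | Interval 1 literal | Interval 1 post-injection | Interval 2 or 3 | Interval 4 |
|---|---|---|---|---|
| a. One record, s = −10, worsens day 5 | in | out | 2: out | in |
| b. One record, s = −10, worsens day 60 | in | out | 2: out | in |
| c. Worsening on day 5 entered as a new record, s = 5 | in | in | 2: in | in |
| d. Non-transplant, s = 10, worsens day 26 (after Dose 2) | in | in | 2: in (10 ≤ 49) | in |
| e. Transplant, s = 60, worsens day 155 | out | out | 3: out (60 < 150) | in |
| f. Transplant, s = 10, worsens day 155 | in | in | 3: out (10 < 150) | in |
| g. Transplant, new record, s = 155 | out | out | 3: in (150 < 155 ≤ 178) | in |

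Reading the rows:

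- Row a is missed by interval 2 whichever way interval 1 is read, and by interval 1 on the post-injection reading.
- Row b shows that the literal reading does not rescue the rule. It puts an event that worsened on day 60 into a 28-day window. The 28-day limit in the TEAE definition does not remove it, because that limit concerns onset.
- Rows e and f show the Dose 2 problem, which does not depend on how interval 1 is read. In row f the worst grade, reached after Dose 2, is tabulated under Dose 1.
- Rows c, d and g are placed acceptably.

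Size of one misplaced subject, at planned maxima (Protocol 4.1; Group A split 2:1) and with no other TEAE in the window:

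- Transplant: 1/15 = 6.7 points.
- Group A Comirnaty: 90 × 1/3 = 30; 1/30 = 3.3 points.
- Group A BNT162b2s01: 90 × 2/3 = 60; 1/60 = 1.7 points.
- Non-transplant immunology subset: 129 − 15 = 114; 1/114 = 0.9 points.

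The two Group A figures apply only if interval 1 is read as post-injection. The documents give no frequency. For an assumed 1 to 5 such subjects the transplant range is 6.7 to 33.3 points (5/15).

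**The case against.** A reader might infer that every TEAE qualifying by worsening falls outside all post-injection intervals and so drops out of the primary proportion. The documents do not support that.

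- Interval 1 has no written lower bound and interval 4 has no date limit. SAP 6.4.1 and 6.4.2 say that the solicited-reaction intervals begin at the injection; 6.4.3 does not say this for TEAEs.
- Protocol 10.3.1.1 lets the worsening of a pre-existing condition be an AE itself, at the investigator's discretion, and 10.3.1.7 foresees AEs documented as a worsening. Such a record would start at the worsening and be placed correctly.
- Protocol 8.3.3 does not settle whether a rise in grade opens a new record or updates the old one.
- For non-transplant subjects, interval 2 spans both doses, so an event arising between them is captured with its worst grade.
- The overall TEAE summary is not restricted to an interval.
- The pool is limited. Events between the trials go to medical history (SAP 6.2), and subjects with an ongoing AE related to a parent-trial vaccine are excluded (Protocol 5.2). In transplant subjects, recording from Visit 5 until Dose 2 is confined to related AEs, AESIs, SAEs and AEs linked to COVID-19.

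Nor can one say that the error always lowers the rate: on the literal reading of interval 1, row b raises it.

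All of this narrows the point without removing it. Separate recording is discretionary, so single records can occur, and for them the written rule gives the results in rows a, b, e and f. Interval 4 cannot stand in for an endpoint defined by 28 days after each injection.

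**Conclusion.** The point holds in limited form. For a worsened event kept as a single record, the start-date rule either omits it from the relevant 28-day interval or, with interval 1 read literally, can count it in the wrong one. The omission from interval 2 (pre-dose start) and from interval 3 (start between the doses) does not depend on how interval 1 is read.

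The number of affected events is unknown and may be small. A proportion changes only for a subject with no other TEAE in the window, and the point sizes assume maximum enrolment. No test is affected, since the trial is descriptive. Because a primary safety endpoint is involved and the transplant group is at most 15 subjects, the correction is worth making.

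**What to change.** In SAP 6.4.3:

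- Keep assignment by start date and time, except that an AE that is treatment emergent because it worsened is assigned by the date and time of worsening.
- Give interval 1 an explicit start at the first injection.
- For the transplant post-Dose 2 interval, also include AEs that started before Dose 2 and worsened within 28 days after it. This is a placement rule only; the protocol's TEAE definition, based on Dose 1, stays as it is.
- If the date of worsening is missing, apply the existing rule for missing dates.

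The cost is a few SAP sentences and minor programming, and TEAE rates may come out slightly less favourable. Guidance to open a new record at each worsening would come late, since Protocol 10.9.3 reports that no parent-trial subjects remain for rollover. The SAP change does not depend on it: applying the worsening route already requires knowing that the worsening came after the injection.

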9.4.2 Primary endpoints

The primary endpoints are defined in Section 3.

All AEs will be coded using the most recent version of Medical Dictionary for Regulatory Activities (MedDRA[®]) coding system to get a system organ class (SOC) and preferred term (PT) for each AE.

Reactogenicity

Solicited local and systemic reactions (from the subject diary) will be summarized using the Safety Set. In general, solicited reactions will be analyzed for each immunization, i.e.:

• Up to 7 d after each IMP injection

For each injection, the number and percentage of subjects reporting at least one local reaction or systemic reaction (i.e., solicited data collected using subject diaries) will be summarized for each of the following types using the Safety Set:

BioNTech SE	Clinical Trial Protocol
Confidential	BNT162-14

- Any local reactions or systemic reactions
- Grade ≥3 local reactions or systemic reactions

Moreover, the number and percentage of subjects reporting at least one local reaction will be summarized by worst grade using the Safety Set.

Unsolicited TEAEs

For Group A and Group B immunology subset, the number and percentage of subjects reporting at least one TEAE (defined in Section 10.3.1) will be summarized by PT nested within SOC for each of the following AE types using the Safety Set:

- Any AE
- Related AE
- Grade of AE
- Related Grade ≥3 AE
- Any solicited AE that continues past 7 d post-trial injection or is an SAE, or AE that fits the definition of a solicited AE but starts after Day 8
- Any SAE
- Related SAE
- AESI

Moreover, the number and percentage of subjects with any AE will be summarized by worst grade by PT nested within SOC.

For Group B, AESIs and SAEs will be analyzed.

Additional AE analyses may be described in the SAP.

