10.3.1.5 Suspected unexpected serious adverse reactions

All suspected adverse reactions related to an IMP that occur in this trial and that are both unexpected and serious are SUSARs. SUSARs are subject to expedited reporting.

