The number and percentage of subjects reporting at least one SAE and the number of SAEs will be summarized by PT nested within SOC for each of the following AE types: Any SAE, Related SAE, fatal SAE and related fatal SAE.

Non-SAEs

The number and percentage of subjects reporting at least one non-SAE and the number of non-SAEs with >5% within any arm or reporting group will be summarized by PT nested within SOC.

AE listings

All TEAEs of subjects that withdrew due to AE, SAEs, and AESIs will be listed. The duration of an AE will be calculated in hours. If for an AE the time is missing then the duration will be calculated in days.

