7.1. Appendix 1: Changes to protocol-planned analyses

Instead of AEs by grade, the overall AE table will include AEs with Grade \geq 3.

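### SAP 6.4.3 equates related TEAEs with SUSARs and omits the protocol's related Grade ≥3 table by SOC and PT; Appendix 1 declares neither change

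*SAP*

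**What the plan says.** SAP 6.4.3 sets out the TEAE types for Group A and the immunology subset of Group B. One of them reads "Related TEAE, i.e., suspected unexpected serious adverse reactions (SUSARs) which will be described in safety reports". Protocol 10.3.1.5 takes suspected adverse reactions related to an IMP and adds that those "that are both unexpected and serious are SUSARs".

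Protocol 9.4.2 says that, in the same two groups, subjects with at least one TEAE "will be summarized by PT nested within SOC for each of the following AE types using the Safety Set". The list that follows includes *Related AE*, "Related Grade ≥3 AE" and *Related SAE*, and ties none of them to SUSARs.

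The SAP's own tables by PT within SOC cover "Any TEAE, Related TEAE, Any TESAE, Related TESAE, TEAEs leading to treatment discontinuation, solicited TEAEs and fatal TEAE". For serious events they cover "Any SAE, Related SAE, fatal SAE and related fatal SAE". A separate set of AE types, including an unglossed *Related AE*, "will be summarized for the above defined AE types for all groups", as overall counts.

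The SAP Introduction says that changes from the protocol are documented in Appendix 1. The single entry there is "Instead of AEs by grade, the overall AE table will include AEs with Grade" ≥3.

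**The concern.** The gloss replaces a broad causality category with a narrow regulatory one. Safety and tolerability are the primary objective, and the table of related events by term is where a reader looks for the profile of reactions attributed to the vaccine. Protocol 8.5 names lymphadenopathy and malaise among the adverse reactions to Comirnaty. Neither is a diary item under Protocol 8.2.4, so both reach the database as unsolicited events. If the SAP is followed to the letter, a non-serious case judged related would appear by term among all TEAEs, but in no SOC/PT table as related.

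A second gap does not depend on the gloss. The protocol's related Grade ≥3 breakdown by term has no counterpart in the SAP's SOC/PT list.

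**Working it through.** No arithmetic figure in the plan needs reproducing: no hypothesis is tested and no sample size was calculated. The check sets the definitions side by side.

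**Step 1. The definitions as sets.** Let R be related, S serious, U unexpected and G Grade ≥3, all within TEAEs.

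- *Related TEAE* as glossed: R and S and U
- *Related TESAE*: R and S
- *Any related Grade ≥3 TEAE*: R and G
- *Related TEAE* without the gloss: R

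The first set lies inside the second, so the type that should be wider can show the smaller count. The third set is not contained in the first. Four kinds of related TEAE show this:

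| Related TEAE | Related TEAE as glossed | Related TESAE | Related Grade ≥3 TEAE | Related TEAE, gloss removed |
|---|---|---|---|---|
| Non-serious, Grade 2 | no | no | no | yes |
| Non-serious, Grade 3 | no | no | yes (overall count only) | yes |
| Serious, expected, Grade 3 | no | yes | yes | yes |
| Serious, unexpected, Grade 3 | yes | yes | yes | yes |

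There is a further internal conflict. SAP 6.4.3 counts an event that starts more than 28 days after the last injection as treatment-emergent only if the investigator judged it related. A late non-serious event can therefore be a TEAE because it is related and still be excluded from *Related TEAE*.

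**Step 2. Protocol against SAP, tables by PT within SOC.**

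| Type in Protocol 9.4.2 | SAP, read literally | SAP, gloss removed |
|---|---|---|
| Related AE | narrowed to SUSARs | kept |
| Related Grade ≥3 AE | absent | absent |
| Related SAE | kept | kept |
| **Kept** | **1 of 3** | **2 of 3** |

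**Step 3. Is either change declared?** The one entry in Appendix 1 concerns AEs by grade in the overall table. It says nothing about what *Related TEAE* means, or about dropping the related Grade ≥3 breakdown by term.

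**Step 4. Who is affected?** Group A and the immunology subset, at the planned maximum 90 + 129 = 219 subjects. Under Protocol Table 3, footnote h, the rest of Group B has only AESIs, SAEs and COVID-19-linked events recorded.

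**Step 5. A minor wording mismatch on intervals.** SAP 6.4 words the TEAE endpoint as following each injection. SAP 6.4.3 gives a Dose-2-only interval to transplant subjects alone. The non-transplant immunology subset is 36 + 30 + 48 = 114 of 129 (88%) at the planned maximum. With injection 2 on Day D and the first interval ending on Day 1 + 28 = Day 29, the first interval holds 29 − D days after injection 2:

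- D = 19 gives 10 days.
- D = 22 gives 7 days.
- D = 25 gives 4 days.

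Counting the injection day as well gives 11, 8 and 5. So the 28-day windows overlap when injection 2 is on schedule. The overlap disappears if injection 2 is delayed well beyond that, as Protocol 7.1.2 allows.

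**The case against.** The strongest reply is that nobody would program the gloss. SAP 6.4.3 opens by referring to Protocol 10.3, which holds both the SUSAR definition and a two-way causality record, related or not related, that ignores seriousness. The same TEAE list carries *Related TESAE* and *Any related Grade ≥3 TEAE*, which make little sense beside a SUSAR-only *Related TEAE*. The parallel AE list has no gloss. The clause about safety reports looks like a stray remark on expedited reporting. This stands: the line is probably a slip. But the SAP gives this type no other wording, and a programmer should not have to guess.

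The second reply is that coverage remains. Related non-serious events still count in the overall *Related AE* row and, if severe enough, in the overall related Grade ≥3 rows. Their terms appear under *Any TEAE*, in the worst-grade tables and, above 5%, in the non-SAE table, though not split by relatedness. This also stands, and it limits the consequence. It does not supply the related Grade ≥3 table by term, which is missing even if the gloss is ignored.

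A reader might infer that every relatedness-based SOC/PT table has been spoiled, since none of the four would show a non-serious event. Three of them are serious-only by name, so that count restates a single table.

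A reader might also infer that events after Dose 2 are lost for non-transplant subjects. They are not: the interval from injection 1 to 28 days after injection 2 covers them. The endpoint tables in both documents do not say *each* for unsolicited TEAEs, and with windows that overlap on schedule, pooling is defensible.

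**Conclusion.** The point holds as a text defect worth correcting. As written, *Related TEAE* contradicts the protocol's SUSAR definition, two other types in its own list and Protocol 9.4.2. Separately, the related Grade ≥3 table by PT within SOC is omitted without being declared. In size, the defect means one table narrowed if the line is taken literally and one table missing under any reading, in up to 219 subjects.

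Confidence is high in the textual conflict and lower that the narrowed table would actually be produced, because that assumes literal programming of a line that is probably a slip. The documents do not support reading this as a flaw in the primary TEAE proportion or as concealment of related events: that proportion, the overall related AE count and the overall related Grade ≥3 counts do not depend on the gloss. The interval mismatch is optional and minor.

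**What to change.** 1. In SAP 6.4.3, replace the glossed line with: *Related TEAE: a TEAE that the investigator judged related to IMP, whatever its seriousness or expectedness*. Mention SUSARs in a separate line.
2. Add *Any related Grade ≥3 TEAE* to the list of tables by PT within SOC, or state in Appendix 1 that this protocol-planned table is dropped, and why.
3. Optional: reconcile the wording of SAP 6.4 with the intervals in 6.4.3, or add a descriptive post-Dose-2 interval for the non-transplant immunology subset. If it is added, use subjects who received injection 2 as denominator and note that days in the overlap count under both doses.

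Items 1 and 2 cost one line of wording plus either one table or one line in Appendix 1. Item 3 costs a wording change or one added set of tables. None of them needs a protocol amendment or new data, because causality and grade are already recorded.
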